### 13.2.1 Analysis of SANDE Questionnaire

The primary and additional analyses for the modify SANDE Questionnaire will be the same as the Glia Ocular Surface Disease Symptoms Questionnaire. Both ANCOVA analyses will be truncated at Visit 5 and any data presented after Visit 5 will be summarized with continuous descripted statistics.

## 13.3 Daily use of eye drops

The daily use of eye drops (e.g. Restasis®, Xiidra®, artificial tears and/or gels, autologous tears) will be collected via subject diary. For each eye, subjects will record the time drops were used, the type of drops used, as well as the number of times drops are administered per wake-time hours and per sleep-time hours.

For each subject and each eye, the average daily use of artificial tears for each week will be calculated as follows:

Weeks are defined relative to the first day of dosing. For example,

Week 1 Day 1 = first day of dosing;

Week 1 Day 2 = first day of dosing + 1;

Etc.

Week 1 Day 7 = first day of dosing + 7;

Week 2 Day 1 = first day of dosing + 8;

Etc.

The sum of the number of times a subject used artificial tears in a given day will be calculated. The average daily frequency for a given week will be the average of the daily sums for all days associated within the same week.

The average daily use of artificial gels will be calculated the same as for artificial tears.

Average daily use of artificial tears and gels will be summarized using continuous descriptive statistics by week and treatment group for each eye separately. Two sample t-tests will be used to compare Pro-ocular to placebo. Artificial tears and gel usage will be summarized and analyzed separately.

Analyses will be performed on the ITT population using observed data only.

All daily use of eye drops (Restasis®, Xiidra®, artificial tears and/or gels, autologous tears) will be presented in a subject listing.

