## SYNOPSIS

Protocol Title:	Treatment safety and efficacy using Pro-ocular™ for chronic ocular graft versus host disease (GvHD) following allogeneic hematopoietic stem cell transplantation
Version / Date:	V 5.1 March 17, 2020
Protocol Number:	oGvHD-1
Study Phase:	2
Study Drug and Placebo:	Pro-ocular™ 1% topical gel (progesterone USP) and placebo
IND Number:	143010
Indication:	Reduce or eliminate ocular symptoms and signs of chronic ocular graft-versus-host disease
Study Objective:	To evaluate the safety and efficacy of Pro-ocular™ 1% topical gel administered twice daily for 70 days in ameliorating symptoms and signs of chronic ocular GvHD.
Design Structure:	Single center, randomized, parallel, double-masked, placebo-controlled study
Institutional Review Board:	Partners Human Research Committee
Duration:	10-week treatment period (active and placebo) 6-week crossover period (placebo to active) open label long term phase to extend the entire treatment period for 27 months
Dosage/Dose Regimen:	Approximately 0.07 g Pro-ocular™ 1% topical gel applied and massaged into the forehead skin twice daily, morning and before bedtime.
Route of Administration:	
Visit Schedule, Double-Masked Phase:	5 visits over 70 days including: 
 
Visit 1, Screening (Day -14 to -1)
 
Visit 2, Baseline and 1st drug application
 
Visit 3, 2-week follow-up (Day 14 ± 2)
 
Visit 4, 6-week follow-up (Day 42 ± 3)
 
Visit 5, 10-week follow-up (Day 70 ± 3)
 

Crossover Phase for Subjects on Placebo:	Subjects in placebo group will receive Pro-ocular 1% topical gel for twice daily administration for over 6 weeks starting at Visit 5:

	
 
• Visit 6, 13-week follow-up (3 weeks on active drug), placebo cross-over subjects only
 
• Visit 7, 16-week follow-up (6 weeks on active drug), placebo cross-over subjects only
 

Long Term Follow Up for Subjects in Open Label Phase (for Eligible & Interested Subjects)	Drug will be supplied after the study period for a total of 27 months' treatment period beginning with Visit 2, with safety monitoring and reporting by the PI and co-investigators under protocol during clinic: Visit 8, 66 ± 6 weeks (15 months) Visit 9, 117 ± 6 weeks (27 months)

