**Table 1. Study Visit Windows**

Study Phase	Scheduled Visit	Planned Study Day	Visit Window
Study Treatment Phase (Double-masked)	Visit 1	Screening/ Day -14	Day -14 to -1
	Visit 2	Baseline/ Day 1, Pre-Dose	N/A
	Visit 2	Day 1, Post Dose	N/A

Study Phase	Scheduled Visit	Planned Study Day	Visit Window
	Visit 3	Week 2/ Day 14	± 2 Day
	Visit 4	Week 6/ Day 42	± 3 Day
	Visit 5	Week 10/ Day 70	± 3 Day
Placebo Cross-over Phase for Subjects on Placebo (Open Label)	Visit 6	Week 13 or Week 3 after active treatment / Day 91	N/A
	Visit 7	Week 16 or Week 6 after active treatment/ Day 112	N/A

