## **8.3 Definition of Baseline**

For the Study Treatment Phase, baseline is defined as the last measurement prior to the first dose of study medication.

For the Cross-over Phase, baseline is defined as the last measurement prior to the first dose of Pro-ocular™ 1% topical gel, which is expected to start on the day after Visit 5.

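### The eye-drop week definition in SAP 13.3 is off by one day: Week 1 holds 8 days and, with 7-day weeks after it, every later week runs one day late against SAP Table 1 (minor)

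*SAP*

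**What the plan says.** SAP 13.3 (Daily use of eye drops) counts weeks from the first day of dosing and gives four anchors as an example:

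- "Week 1 Day 1 = first day of dosing"
- "Week 1 Day 2 = first day of dosing + 1"
- "Week 1 Day 7 = first day of dosing + 7"
- "Week 2 Day 1 = first day of dosing + 8"

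The rule for combining days is: "The average daily frequency for a given week will be the average of the daily sums for all days associated within the same week". Tears and gels are then summarized by week and treatment group for each eye, and the arms are compared with two-sample t-tests.

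The study-day scale is set in SAP Table 1, where Visit 2 is "Baseline/ Day 1, Pre-Dose", Visit 3 is Week 2 and Day 14, Visit 4 is Week 6 and Day 42, and Visit 5 is Week 10 and Day 70. The protocol synopsis agrees: "Visit 5, 10-week follow-up (Day 70 ± 3" days). For the placebo group, SAP 8.3 speaks of the first dose of active gel, "which is expected to start on the day after Visit 5".

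**The concern.** The first two anchors use one convention (offset equals day number minus one) and the third uses another (offset equals day number). Both cannot hold within the same week. The fourth anchor carries the extra day into Week 2.

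This text is the derivation rule for a set of weekly tables and t-tests. A programmer who follows it literally gets an 8-day first week and displaced later weeks. One who silently repairs it gets different tables. Independent programming could therefore disagree, and the week labels in the eye-drop table would not line up with the visit weeks used elsewhere in the SAP.

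**Working it through.** **Inputs.** The four anchors and the averaging rule come from SAP 13.3. Day 1 as the first dosing day comes from SAP Table 1, so study day = offset + 1. Visit 5 on Day 70 ± 3 comes from the protocol synopsis and SAP Table 1. The first active dose on the day after Visit 5 comes from SAP 8.3 and section 12.

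**Step 1: the printed figure.** Day 1 = +0 and Day 2 = +1, so Day d = d − 1. Then Day 7 = 7 − 1 = +6, and the next day, Week 2 Day 1, is +7. The SAP prints +7 and +8, so its figures are not reproduced.

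**Step 2: length of Week 1 as printed.** Week 1 starts at offset 0 and Week 2 at offset 8. Offsets 0 to 7 make 8 days, study Days 1 to 8.

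**Step 3: later weeks.** The SAP does not list them, so an assumption is needed: weeks of 7 days after Week 1.

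- As printed, week k (k ≥ 2) covers offsets 7k − 6 to 7k, which are study Days 7k − 5 to 7k + 1.
- With +6 and +7, week k covers offsets 7(k − 1) to 7k − 1, which are study Days 7k − 6 to 7k.

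| Week | As printed | With +6 and +7 | Day in SAP Table 1 |
|---|---|---|---|
| 1 | 1–8 | 1–7 | none |
| 2 | 9–15 | 8–14 | 14 |
| 6 | 37–43 | 36–42 | 42 |
| 10 | 65–71 | 64–70 | 70 |

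The corrected offsets end each tabulated week on the Table 1 day. If the 8-day pattern were instead repeated every week, Week 10 would cover Days 73 to 80, which is further out of line.

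**Step 4: effect on a weekly mean.** Let m be a subject's mean over Days 1 to 7 and x the use on Day 8. The printed Week 1 mean is (7m + x)/8 = m + (x − m)/8. For a later week, one day leaves and one enters, so the mean changes by (entering day − leaving day)/7. The documents give no figures for day-to-day variation in drop use. As an illustration, a difference of one application moves the mean by 1/8 = 0.125 in Week 1 and by 1/7 = 0.14 in a later week.

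**Step 5: overlap with the cross-over, if diary days were not split by phase.** Days on or after Visit 5 + 1 that fall in Week 10:

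| Visit 5 | First active day | Printed Week 10 (65–71) | Corrected Week 10 (64–70) |
|---|---|---|---|
| Day 67 | 68 | 4 | 3 |
| Day 70 | 71 | 1 | 0 |
| Day 73 | 74 | 0 | 0 |

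With Visit 5 on Day 67, correcting the offsets removes only one of the four overlapping days. The visit window matters more than the off-by-one.

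**The case against.** The strongest counter-case accepts the miscount and disputes that it matters.

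- **The result is a mean of daily sums, not a total.** An 8-day Week 1 still estimates use per day. The shift is the same in both arms, so it favors neither. This stands.
- **The variable is not a key one.** SAP 2.2 lists eye-drop use under additional efficacy variables. The Benjamini-Hochberg adjustment in SAP 8.5 covers the key variables only, and the daily data will be listed in full. This stands.
- **The later weeks are extrapolated.** The SAP gives examples and leaves the rest to be continued, so Day 71 as the end of Week 10 rests on an assumed 7-day continuation. This stands as a condition. It does not touch the 8-day Week 1, which follows from the printed anchors alone.

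A reader might go further and infer that Week 10 puts a placebo subject's first day on active drug into the masked comparison, since that day is nominally Day 71. The documents do not support this as a planned consequence. SAP 3.1 and the opening of section 13 require separate analyses by phase, SAP section 6 limits the first database lock to data up to Visit 5, and SAP section 16 makes all cross-over data descriptive. What remains is a gap in wording. SAP 13.1, 13.2 and 13.4 each truncate their comparisons at Visit 5, while 13.3 does not, and nothing says how a week straddling Visit 5 is cut.

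**Conclusion.** The definition is wrong as written, and nothing elsewhere in either document corrects it. Week 1 holds 8 days. Given 7-day weeks after that, Weeks 2 to 10 each start and end one day late, and Weeks 2, 6 and 10 miss their Table 1 days by one.

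Severity is minor. The effect on weekly mean use should be small unless use changes sharply from one day to the next, and the same displacement applies to both arms. With phase separation applied and Visit 5 on Day 70, the printed Week 10 would average 6 masked days (65 to 70) in place of 7. Active-drug days would enter the placebo arm's Week 10 only if the phase split and the lock at Visit 5 were not applied to diary days. Even then the number would run from 0 to 4, depending mainly on when Visit 5 fell. No bias in the treatment comparison has been shown.

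**What to change.** In SAP 13.3:

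1. Give Week 1 Day 7 an offset of +6 and Week 2 Day 1 an offset of +7, and state that every week has 7 days.
2. Add that the weekly comparisons are truncated at Visit 5, as 13.1, 13.2 and 13.4 already provide for their own analyses, and that diary days after Visit 5 belong to the Cross-over Phase.
3. State where masked days after Day 70 go when Visit 5 is late (Days 71 to 73): either a partial Week 11 or an addition to Week 10.

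The cost is two numbers, two or three sentences, and the matching derivation code. No data collection or other analysis changes.

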**Evaluation Criteria:**

Efficacy Measures:	
Glia Ocular Surface Disease Symptoms Questionnaire, Clinic and Daily Diary
 
 
- Ocular discomfort
 
- Dryness
 
- Grittiness
 
- Burning
 
- Stinging
 
- Foreign body sensation
 
- Ocular pain
 
- Conjunctival redness
 
- Itching
 
- Photophobia
 
- Mucus discharge
 
- Blurred or cloudy vision
 
- Air flow sensitivity
 
- Lid redness
 
- Lid sticking
 
 
Daily use of eye drops (Restasis®, Xiidra®, artificial tears and/or gels, autologous tears (# times administered per wake-time hours and sleep-time hours)
 
SANDE – Symptom Assessment iN Dry Eye Questionnaire
 
National Institutes of Health Eye Score
 
Chronic ocular GvHD Signs (Ophthalmologist examination at each visit)
 
 
- TearScan examination: Tear film, lid margins, and meibum expression
 

---------------------------	---

	
 
- Visual acuity with current correction.
 
- Slit lamp without staining: Lids (lid margin erythema, edema, ulceration, notches, entropion/ectropion, trichiasis/madarosis, floppy eyelids, hordeolum); Conjunctiva (hyperemia, cicatricial changes, pseudomembranes, chalasis); Cornea (edema, ulcers, filamentous keratitis, thinning, corneal neovascularization, scars, conjunctival epithelium invasion, limbal thickening).
 
- Corneal and conjunctival fluorescein staining
 
 
Non-Ocular GvHD Signs (recorded by patient and physician):
 
 
- Systemic assessment by BMT physician such as dry mouth
 

Safety Measures:	
 
- Adverse events
 
- Visual acuity
 
- Slit lamp biomicroscopy
 
- Undilated fundoscopy examination
 
- Intraocular pressure
 
- Systemic assessment by BMT physician at Dana Farber Cancer Institute
 

Laboratory Tests Routine and Afor Assessment of HPA (hypothalamic-pituitary-adrenal axis) Function	
Tests to be run at Visits 1, 4, 5, 7, 8 and 9: Standard panel to include CBC with differential, metabolic panel, tacrolimus/sirolimus levels, Vitamin D Total 25-hydroxy (D2 and D3), T4 (T total and free), T3, ACTH, TSH, DHEA-S, estradiol, FSH, LH, progesterone, testosterone (total and free).

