**The evaluation criteria are as follows:**

Efficacy Measures:	
Glia Ocular GvHD Symptoms Questionnaire      Clinic Daily Diary
 
 
- Ocular discomfort
 
- Dryness
 
- Grittiness
 
- Burning
 
- Stinging
 
- Foreign body sensation
 
- Ocular pain
 
- Conjunctival redness
 
- Itching
 
- Photophobia
 
- Mucus discharge
 
- Blurred or cloudy vision
 
- Air flow sensitivity
 
- Lid redness
 
- Lid sticking
 
 
Use of eye drops (Restasis®, Xiidra®, artificial tears and/or gels, autologous tears, # times administered per wake-time hours and sleep-time hours)
 
SANDE – Symptom Assessment iN Dry Eye Questionnaire
 
National Institutes of Health Eye Score
 
Ocular GvHD Signs (physician examination at each visit)
 
 
- TearScan examination: Tear film, lid margins, and meibum expression.
 
- Visual acuity with current correction.
 
- Slit lamp without staining: Lids (lid margin erythema, edema, ulceration, notches, entropion/ ectropion, trichiasis/madarosis, floppy eyelids, hordeolum); Conjunctiva (hyperemia, cicatricial changes, pseudomembranes, chalasis); Cornea (edema, ulcers, filamentous keratitis, thinning, corneal neovascularization, scars, conjunctival epithelium invasion, limbal thickening).
 
- Corneal and conjunctival fluorescein staining
 
 
Non-Ocular GvHD Signs (recorded by patient and physician):
 
 
- Systemic assessment by BMT physician such as dry mouth
 

Safety Measures:	
 
- Adverse events
 
- Visual acuity
 
- Slit lamp biomicroscopy
 
- Undilated fundoscopy examination
 
- Intraocular pressure
 
- Systemic assessment by BMT physician at Dana Farber Cancer Institute
 

Laboratory Tests Routine and for	
Tests to be run at Visits 1, 4, 5, 7, 8, and 9: CBC with differential, metabolic panel, tacrolimus/sirolimus levels,

Assessment of HPA (hypothalamic-pituitary-adrenal axis) Function	Vitamin D Total 25-hydroxy (D2 and D3), T4 (Total and free), T3, ACTH, TSH, DHEA-S, estradiol, FSH, LH, progesterone, testosterone (total and free).
---	--

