**VIII. POTENTIAL BENEFITS****a. Potential benefits to participating individuals**

The potential benefits to participating individuals are reduction or elimination of ocular discomfort, especially the extreme pain experienced by many ocular GvHD patients, and ocular tissue damage repair, potentially preventing progression to when surgical procedures may be required.

Another potential benefit is the reduction of use of artificial tears and other eye drops that only provide temporary relief.

There is potential improvement of the overall quality of life, and enabling the return to normal daily living, sleep, work, and other activities.

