### 2.1 Study Variables

### 2.2 Efficacy Variables

The key efficacy variables include the following:

- GLIA Ocular Surface Disease Questionnaire taken at the clinic
- Modified Symptom Assessment in Dry Eye Questionnaire (SANDE) taken at the clinic

Additional efficacy variables include the following:

- Chronic Ocular GvHD Signs including the following:
  - TearScan Examination
  - Visual acuity with current correction
  - Slit lamp biomicroscopy without staining:

- Lid Edema, Lid Erythema, Lid Margin Ulceration and Conjunctival Hyperemia are of interest however all ocular regions will be analyzed similarly
  - Corneal and conjunctival fluorescein staining
  - Facial Presentation and Blinks per Minute
- Daily diary GLIA Ocular Surface Disease Questionnaire
- Daily use of eye drops
- National Institutes of Health (NIH) Eye Score

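### SAP 13.3 compares the arms on artificial tears and on gels, each alone; autologous tears, Restasis and Xiidra get no frequency analysis, and no total is formed

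*SAP*

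**What the plan says.** The protocol treats eye-drop use as a single efficacy measure. The synopsis gives it as "Daily use of eye drops (Restasis®, Xiidra®, artificial tears and/or gels, autologous tears", counted over waking and sleeping hours, and the evaluation criteria in Section V repeat it. Section VIII.a describes the hoped-for benefit just as broadly: "Another potential benefit is the reduction of use of artificial tears and other eye drops that only provide temporary relief".

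SAP 2.2 lists "Daily use of eye drops" among the additional efficacy variables, not the key ones. Under SAP 13.3, collection is complete: "The daily use of eye drops (e.g. Restasis®, Xiidra®, artificial tears and/or gels, autologous tears) will be collected via subject diary". Derivation is narrower. For artificial tears, "The sum of the number of times a subject used artificial tears in a given day will be calculated", and the daily sums are averaged by week. For gels, "The average daily use of artificial gels will be calculated the same as for artificial tears". Each result is summarised by week, arm and eye and compared with a two-sample t-test, and "Artificial tears and gel usage will be summarized and analyzed separately". The remaining drop types appear only in a subject listing.

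**The concern.** Three of the drop types named in the protocol's measure have no frequency summary or test, and nothing adds the types together. Protocol Section VII lets subjects keep using other ocular medications alongside the gel, and no rule in SAP 13.3 deals with a change of type. Each analysed variable therefore mixes two things: how often subjects need drops, and which product they choose. Product choice is made after randomisation and may respond to symptoms, so it could differ by arm. If it does, a difference in artificial-tear or gel use between arms need not be a difference in drop use. The question that the protocol's measure poses, whether subjects use fewer drops, would rest on two partial counts.

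**Working it through.** The plan gives no effect size, SD or switching rate for drop use, so there is no figure of its own to reproduce.

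**Inputs from the documents.** Allocation 22:11 (SAP 5); two-sided 0.05, differences taken as active minus placebo (SAP 8.4); weekly means and two-sample t-tests (SAP 13.3). All counts, SDs and switching rates below are assumptions.

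**1. Coverage of each drop type**

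| Drop type | In diary | Weekly mean and t-test | Other output by arm |
|---|---|---|---|
| Artificial tears | yes | yes | users, if recorded as a concomitant medication |
| Gels | yes | yes, separately | same |
| Autologous tears | yes | no | same |
| Restasis, Xiidra | yes | no | same |
| Total | not formed | no | none |

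The concomitant-medication tables (SAP 11.2, Table 14.1.4.1) count subjects using a product, not applications per day. SAP Section 16, which lists departures from the protocol, does not mention the narrowing. The SAP was written against protocol version 4.0 and the version supplied is 5.1, so that silence carries only limited weight.

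**2. What one switch does, at a constant 6 applications a day (assumed)**

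| Switch | Artificial tears | Gels | Tears + gels | All types |
|---|---|---|---|---|
| Tears to autologous | −6 | 0 | −6 | 0 |
| Tears to gel | −6 | +6 | 0 | 0 |
| Gel to tears | +6 | −6 | 0 | 0 |

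Only the first row has no offset in an analysed variable.

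**3. Effect on an arm mean.** If s subjects in an arm of n each move k applications a day to an unanalysed type, the analysed mean falls by s × k/n. With k = 4 (for example, from 6 artificial tears to 2 artificial plus 4 autologous):
- placebo, s = 1: 4/11 = 0.36 a day; s = 2: 8/11 = 0.73 a day;
- active, s = 2: 8/22 = 0.36 a day.

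Switching in the placebo arm makes active minus placebo more positive and can hide a benefit. Switching in the active arm makes it more negative and can look like one.

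**4. Effect on the test.** An illustrative simulation used 22 against 11 subjects, 40,000 replicates per scenario, gamma-distributed daily use and equal total use in both arms. The assumed mean (SD) was 4 (3), 6 (3) or 8 (4) a day. Switchers moved all their use to an unanalysed type. The expected spurious difference is −(p_active − p_placebo) × mean; with 25% against 0% and a mean of 6 that is −1.5, and the simulation gave −1.49.

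| Switching, active / placebo | Artificial-tear t-test rejects | Total over all types rejects |
|---|---|---|
| 0% / 0% | 4.7–5.0% | 4.7–5.0% |
| 10% / 10% or 25% / 25% | 4.8–5.1% | 4.7–5.0% |
| 10% / 0% | 6–7% | 4.6–5.0% |
| 25% / 0% | 14–19% | 4.8–5.0% |
| 50% / 0% | 46–63% | 4.8–5.0% |

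In the 25% / 0% and 50% / 0% rows essentially all rejections favour active, because only active subjects were made to switch.

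**The case against.** Reporting tears and gels separately is a legitimate choice. The protocol lists the drop types but never defines a total, so no pre-specified sum was dropped. Drop use is in neither hypothesis of SAP 2.5, and Section VIII.a describes a possible benefit to participants, not a trial claim. Protocol Section VII speaks of continuing other ocular products and does not mention starting or exchanging them, and no switching rate is given. All of this stands, and it limits the weight of the point.

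Three stronger readings are tempting, and the documents do not support them:

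- *Any change of drop type counts as less use.* Not so for tears and gel: both are analysed, and the fall in one is matched by a rise in the other. A move from autologous to artificial tears would raise an analysed count.
- *A subject who changes product is scored as improved.* SAP 13.3 computes no change from baseline and no subject-level score; it compares weekly arm means. The schedule first dispenses the diary after the first dose at Visit 2, so no pre-dose diary count is planned. Nor do the documents say that autologous tears are a step up in treatment.
- *The other products are never summarised.* If recorded as concomitant medications they appear by arm as numbers of users, and every type is listed by subject. What is missing is their daily frequency.

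The objection leaves one gap. Autologous-tear frequency is collected but not analysed, so a move to it from artificial tears or gels is offset nowhere. Separate tear and gel tables do not close that gap. The NIH eye score's own cut-point, lubricant drops up to three or more than three times a day, also treats lubricants collectively.

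**Conclusion.** The point holds in a limited form. The two analysed counts do not cover the measure that the protocol names, and a shift of use into autologous tears (or Restasis or Xiidra) lowers an analysed arm mean without compensation. Bias in the treatment comparison requires switching that differs by arm, and its direction cannot be determined from the documents. With equal switching the test stays near 5%, although the variable still does not measure total drop use. The sizes shown (0.36 to 0.73 applications a day; 6–7% rejection at one-sided switching of 10%, up to 46–63% at 50%) rest wholly on assumed counts, SDs and switching rates and are not predictions for this trial. For tears against gel, the defect is only that no total reconciles the two results. This is a minor point on an additional efficacy variable; the GLIA and SANDE conclusions do not depend on it.

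**What to change.** In SAP 13.3 and Table 14.2.6:

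- add total lubricant applications per day per eye, defined as artificial tears plus gels plus autologous tears over waking and sleeping hours, averaged by week and compared between arms in the same way as the present variables;
- keep artificial tears and gels as components, and add autologous tears as a third;
- give a by-arm frequency summary of Restasis and Xiidra. They stay outside the lubricant total, so a move to either would still lower it, and this summary is what would show that;
- note the change in SAP Section 16. If it is made only after unmasking, label it as an additional analysis in the study report.

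The cost is SAP wording and one or two extra tables. No new data are needed, because the diary already records type and number by eye. The drawback is that a total gives equal weight to lubricants that may not be equivalent, which is why the components should be shown beside it.
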